5.5 Method for assigning subjects to treatment group

Randomisation will be stratified according to ALOX5 promoter polymorphism status. This will yield two genotype groups:

[figure not shown]
Group I Children with the [5/5] ALOX5 promoter polymorphism genotype. **Group II** Children with [5/x and x/x]" ALOX5 promoter polymorphism genotype; where x is > or < than 5 SP1 repeats. (Groups will be referred to as Stratum A or B – all trial staff will be blinded to this relationship except the laboratory technician).

For children (participants) in each of these two genotype groups (strata) we will assign consecutive randomisation numbers from randomised permuted blocks of 10. Within each block equal numbers of children will be randomly allocated to placebo and active treatment. When all numbers from the first block have been assigned a new block of randomisation numbers will be allocated to that stratum, until a total of 1300 children in the two strata combined have been assigned a randomisation number. If a randomisation number is assigned to a child who does not subsequently take any dose of IMP, the IMP bearing that randomisation number will be returned to pharmacy, and the randomisation number may be assigned to another child (participant) provided that that medication has not been dispensed.

[figure not shown]
WAIT Trial_ Protocol_v7_24th June 2011

[figure not shown]
Page 24 of 58

5.6 Flow diagrams

^{*}Randomisation key provided by manufacturer, held in sealed envelope by Pharmacist and Data Monitoring Committee

5.7 Follow-up procedures

Parents will be contacted at the following times post-randomisation:

- **+Two months: Telephone call:** a research nurse or research assistant will telephone the subject to check whether the parent has initiated the IMP, the numbers of days the IMP was used, use of healthcare resources, concomitant medications, procedures, days lost from childcare, and parent days lost from work. Parents will also be asked if their child experienced any adverse events, and these will be recorded if so.
- **+Four months: Telephone call:** a research nurse or research assistant will telephone the parent to check whether the parent has initiated the IMP, the numbers of days the IMP was used, use of healthcare resources, concomitant medications, procedures, days lost from childcare, and parent days lost from work. Parents will also be asked if their child experienced any adverse events, and these will be recorded if so.
- **+Six months: Telephone call:** a research nurse or research assistant will telephone the parent to check whether he/she has initiated the IMP, the numbers of days the IMP was used, use of healthcare resources, concomitant medications, procedures, days lost from childcare, and parent days lost from work. Parents will also be asked if their child experienced any adverse events, and these will be recorded if so.
- **+Eight months: Telephone call:** a research nurse or research assistant will telephone the parent to check whether he/she has initiated the IMP, the numbers of days the IMP was used, use of healthcare resources, concomitant medications, procedures, days lost from childcare, and parent days lost from work. Parents will also be asked if their child experienced any adverse events, and these will be recorded if so.
- **+Ten months: Telephone call:** a research nurse or research assistant will telephone the subject to check whether the parent has initiated the IMP, the numbers of days the IMP was used, use of healthcare resources, concomitant medications, procedures, days lost from childcare, and parent days lost from work. Parents will also be asked if their child experienced any adverse events, and these will be recorded if so.
- **+Twelve months: Telephone call:** a research nurse or research assistant will telephone the subject to check whether the parent has initiated the IMP, the numbers of days the IMP was used, use of healthcare resources, concomitant medications, procedures, days lost from childcare, and parent days lost from work. Parents will also be asked if their child experienced any adverse events, and these will be recorded if so. Parents will be asked to return their used IMP box containing unused and used sachets.

Visit 3 where appropriate: to replace expired/exhausted medications
Visit 3 in a subgroup of 30 families: A research assistant will visit the
home of 30 families to establish their attitudes towards genetic testing in order to individualise
therapy, acceptability of parent-initiated therapy for preschool wheeze, their experience of
using the trial medication, and any difficulties/advantages of the parent-initiated approach.

Parents will contact the research nurse or research assistant at the following times post-randomisation:

Parents will be asked to contact the research nurse should they have any concerns regarding the medication, or when they are running short of medication. Data will be recorded in a follow up telephone call from the research nurse to include the number of days of wheeze, GP attendance, admission to hospital, need for additional asthma therapy, adverse events, procedures, days lost from childcare, and parent days lost from work, the nurse will request that the diary card be sent back if this has not already occurred. This researcher phonecall will not occur until at least 10 days following the parent phonecall in order not to influence the primary outcome. If a parent mislays or exhausts the IMP supplied, the research team will contact their local pharmacy with details of that child's randomisation number, and ask them to supply a replacement box of IMP containing active or placebo medication according to that subject's randomisation number. The research team shall remain blinded to active/placebo allocation.

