10.1.3 Study definitions

- **1. Need for unscheduled medical attention** will be defined as an episode requiring an unscheduled attendance to either a general practitioner, or to an accident and emergency department, or a combination of both where wheeze is diagnosed by a clinician.
- **2. Time from randomisation to first attack of severe wheeze** will be defined as the number of days from the date of administration of first dose of IMP to the first date on which a wheeze exacerbation attains criteria of severity stated in 1 above.
- **3. Number of days with parent-reported wheeze** will be defined as the number of days with wheeze over the 12 month trial period obtained by telephone contact with the researcher and diary card.
- **4.** Use of inhaled relief medication, expressed as total number of occasions used over **12 month period**, and mean number per wheeze episode will be obtained from the number of actuations calculated by diary card reporting.

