10.8 Secondary endpoint analysis

A Poisson regression analysis with a random effect for individuals to allow for over-dispersion will be applied to determine the influence of allocation on number of days with parent-reported wheeze, number of admissions to hospital, number of admissions to hospital > 4 hrs duration. An incident rate ratio for each factor will be presented with 95% confidence intervals.

Time to first attack of wheeze will be analysed using a log-rank test with adjustment for clustering and, if hazards are proportional, Cox's proportional hazards models adjusting for clustering. In a Cox model, strata and centre will be included as covariates.

Other continuous variables will be analysed with analysis of covariance. Dichotomous variables will be analysed with logistic regression analysis.

Adverse events will be analysed with descriptive statistics.

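### Section 5.7 gives no routine route for collecting wheeze days or diary cards: both are asked for only in a parent-triggered call, so their ascertainment is partly selective

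*Protocol*

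**What the plan says.** Protocol 5.7 describes six scheduled calls, at two-month intervals from +2 to +12 months (T1 to T6 in the 3.1 schema). Their listed content is essentially the same each time: whether the IMP was started, then "the numbers of days the IMP was used, use of healthcare resources, concomitant medications, procedures, days lost from childcare, and parent days lost from work", plus adverse events. The twelve-month call adds one request: "Parents will be asked to return their used IMP box containing unused and used sachets".

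The same section then describes a further contact. Parents are to ring the research nurse "should they have any concerns regarding the medication, or when they are running short of medication". A return call follows, at least 10 days later: "Data will be recorded in a follow up telephone call from the research nurse to include the number of days of wheeze, GP attendance, admission". In that call "the nurse will request that the diary card be sent back if this has not already occurred".

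In 10.1.3, item 3 defines parent-reported wheeze days as "the number of days with wheeze over the 12 month trial period obtained by telephone contact with the researcher and diary card". Section 10.8 plans a Poisson regression with a random effect for the "influence of allocation on number of days with parent-reported wheeze". Section 10.1.2 also lists duration and severity of episodes by diary card, and salbutamol use per episode from the diary card.

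**The concern.** Followed as written, 5.7 asks every family about healthcare use and IMP use, but asks about days of wheeze only if the parent has first made contact about a concern or a shortage. The diary card, the second source, is requested only in that same call.

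Running short is not a neutral trigger. It depends on how many courses the child has used since randomisation. Wheeze starts courses, and montelukast is expected to reduce wheeze, so fewer treated children may reach the trigger. A comparison of arms among children who were asked then compares groups selected after randomisation. An analysis plan cannot put this right later, because it cannot recover answers to questions that were never asked. The reminder has the same weakness for the other diary-based secondary endpoints.

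**Working it through.** **Passages side by side**

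| Item | Scheduled calls T1 to T6 (5.7) | Extra call (5.7) | Needed by |
|---|---|---|---|
| Days of wheeze | not listed | listed | 10.1.3 item 3; 10.8 |
| Request for diary card | not listed; T6 asks only for the IMP box | listed, if not yet returned | 10.1.3 items 3 and 4; 10.1.2 |
| Healthcare use, days lost | listed | listed | 10.1.2 |

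The 3.1 schema has no row for wheeze days or for diary return.

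**When the shortage trigger fires.** A box holds 50 sachets (5.2.5). A course is one sachet a day for 10 days, started for a cold or for wheeze (5.4). So 50 / 10 = 5 courses exhaust a box. Planned supply is 2600 boxes for 1300 children (5.3), or 2600 / 1300 = 2 boxes per child on average.

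**How many children reach five courses.** The protocol gives no course rate and no figure of its own on this point. Its only event rate is the attack mean 0.76 with SD 1.22, falling to 0.51 on treatment (10.2.1). The implied dispersion is (1.22² − 0.76) / 0.76² = 1.26. If attacks alone used up courses, the negative binomial probability of five or more in a year would be 1.9% on placebo and 0.6% on montelukast. Colds start courses too, so the real share is higher. Assuming 2 to 8 courses a year and dispersion 0 to 1.26:

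| Arm | P(at least 5 courses) |
|---|---|
| Placebo | 5% to 90% |
| Courses cut by 10% | 4% to 84% |
| Courses cut by 33% | 1% to 62% |

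**Illustrative bias with no diaries from untriggered families.** The quantity is E[wheeze days | courses ≥ threshold, active] / E[wheeze days | courses ≥ threshold, placebo], with a true ratio of 0.67. All rates below are assumptions.

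- *Model A, wheeze and colds separate.* Wheeze episodes are Poisson with gamma frailty (shape 1), colds are Poisson and unaffected by treatment, and there are 4 wheeze days per episode. With 2 of each per year and a trigger at 5 courses, 34% of placebo and 25% of montelukast children are asked, and the ratio among them is about 0.77. With means of 1.5 to 3 for each and a trigger at 4 or 5 courses, 21% to 73% of placebo and 13% to 66% of montelukast children are asked, and the ratio is 0.71 to 0.80. With 0.76 wheeze episodes and 4 colds it is 0.68, almost unbiased.
- *Model B, wheeze days proportional to courses and treatment cutting all courses by 33%.* With dispersion 0.3 and a trigger at 5 courses, the ratio is 0.91, 0.89 and 0.84 at means of 3, 4 and 6 courses. This is harsher, because it lets treatment reduce colds, which the protocol does not claim.

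**Letting untriggered families return diaries at random.** In the Model A base case, 25% return gives 0.69 and 50% return gives 0.67. Rerunning Model B with the same return shares gives 0.65 to 0.74 at 25% and 0.64 to 0.70 at 50%.

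**The case against.** The strongest reply is that the diary card is a separate source for every family. Section 5.4 has parents recording vomited doses on a diary chart, 10.1.2 treats the diary as a general record, and the reminder is conditional on the card not having come back already, so some cards must return by another route. A selective reminder is not the same as selective capture. This stands in part. A reader might infer that wheeze days are captured mainly in children with many episodes, and the documents do not support that. Medication concerns are a second trigger, two boxes per child are planned so a resupply contact may be common, and the share reaching five courses cannot be fixed. What remains is that 5.7 describes no routine return of cards, so neither the return rate nor its randomness can be assumed.

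The second reply is that the protocol's lists are not exhaustive. The CRF list in 8.3 omits adverse events although 7.4 records serious adverse events there, and the 3.1 schema has no row for days lost from work or childcare, which every call collects. So a missing schema row proves little by itself. But 5.7 gives six nearly identical lists without wheeze days and then one list with them, which reads as a difference in content.

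A reader might also infer an exaggerated effect from counting unasked children as having zero wheeze days. In the Model A base case that would give (0.253 / 0.345) × 0.77 = about 0.56. No section proposes it. Each scheduled call records IMP use, so a child with one to four courses would not look episode-free, and handling of missing data may properly sit in the analysis plan.

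Finally, the reach is limited. Wheeze days are defined in 10.1.3 and analysed in 10.8 but are not listed in 10.1.2, and the primary outcome does not use them.

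**Conclusion.** The gap between 5.7 and what 10.1.3 and 10.8 require is real. Taken as written, the telephone component of the wheeze-day measure and the diary-card reminder reach only families who made contact, partly according to course use that treatment may change.

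The size of any bias is not determinable from the protocol. Roughly 0.7 to 0.9 in place of a true 0.67 is a worst case that rests on assumed episode rates and on no diaries from untriggered families. The direction is attenuation among those asked, and random diary return by a quarter to a half of the other families removes most of it. Non-random return could behave differently.

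The measures affected are wheeze days and the diary-based secondary endpoints. The primary outcome (10.1.1), confirmed from clinical records, and the sample size are untouched. The change should be made, but the trial's main conclusion does not hang on it.

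**What to change.** - In 5.7, add two items to each of T1 to T6 for all children: number of days of wheeze since the last scheduled call, and a request to return completed diary cards. Add a matching row to the 3.1 schema.
- In 10.1.3 item 3, derive wheeze days from these scheduled calls and the diary cards. State how data from the parent-triggered call are used so that no day is counted twice.

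The cost is protocol and call-script wording, and one or two more questions in calls that already take place. Calls become slightly longer, and two-month recall brings some error, expected to be similar in both arms. If the call scripts already ask these questions, only the text of 5.7 needs aligning.

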5.4 Treatment procedures

IMP will be presented as white granules administered either directly in the child's mouth, or mixed with a spoonful of cold or room temperature soft food (e.g., applesauce, ice cream, carrots and rice). The white sachet containing the granules should not be opened until ready to use. After opening the sachet, the full dose of granules must be administered within 15 minutes. If mixed with food, the granules must not be stored for future use. The granules are not intended to be dissolved in liquid for administration. However, liquids may be taken by the child subsequent to administration. The granules can be administered without regard to the timing of food ingestion. The dose is 1 sachet per day, started when the child has evidence of a viral cold or has wheeze, and stopped after 10 days. If a child vomits after the administration of the IMP no additional dose is given, and parents record this on the diary chart.

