7.4.2 Unexpected SAEs

Unexpected SAEs will be recorded in the CRF and on the sponsor SAE form and reported to the JRO within one working day of the PI or co-investigators becoming aware of the event. The co-investigators listed in this protocol/appendix will be authorised to sign the SAE forms in the absence of the PI. SUSARs arising during the trial will be reported to the JRO and the main REC within one working day of the PI or co-investigator becoming aware of the event.

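### Section 5.7 holds back the call that records adverse events for at least 10 days after a parent rings with a medication concern, with no exception for a suspected reaction

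*Protocol*

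**What the plan says.** Section 5.7 of the protocol ends with contacts that parents start themselves: "Parents will be asked to contact the research nurse should they have any concerns regarding the medication, or when they are running short of medication". It then says where the information goes: "Data will be recorded in a follow up telephone call from the research nurse to include the number of days of wheeze". The list of items continues with GP attendance, hospital admissions, and "need for additional asthma therapy, adverse events, procedures, days lost from childcare". The next relevant sentence sets the timing: "This researcher phonecall will not occur until at least 10 days following the parent phonecall in order not to influence the primary outcome". Nothing in the section separates a call about low supply from a call about a possible reaction.

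Two other places matter. Section 5.4 fixes the course: one sachet a day, "started when the child has evidence of a viral cold or has wheeze, and stopped after 10 days"; sections 6.1 and 6.5 give the same length. Section 7.4.2 requires unexpected SAEs to be "reported to the JRO within one working day of the PI or co-investigators becoming aware of the event", and sets the same one-working-day limit, from the same starting point, for reporting SUSARs to the JRO and the main REC.

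Routine collection is separate. At each two-monthly call, "Parents will also be asked if their child experienced any adverse events, and these will be recorded if so". The schedule in section 3.1 places adverse event recording at visit 2, at the six telephone calls and at visit 3, with no entry for a call that the parent makes.

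**The concern.** The hold has a sensible purpose. The primary outcome is a count of unscheduled attendances, and a nurse asking about symptoms and attendance mid-episode could change what the parent does next. The difficulty is its breadth: adverse events are in the same list as the outcome items, so the delay covers them too.

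Three things are at stake. First, data quality: onset, severity and relation to dosing are asked about at least 10 days after the parent thought the matter worth a telephone call. Section 9.1.3 relies on DMC review of accumulating adverse event data as a protection for the children, so the quality of those data matters. Second, decisions that depend on an investigator knowing of the event, namely stopping study medication under section 6.7 item 2 and requesting a code break under section 5.10, have no stated feed from the parent's call. Third, the expedited reports in section 7.4.2 begin only once an investigator knows, so a late recording step with no stated hand-over can push that starting point back.

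**Working it through.** The protocol states no figure for this point, so there is none to reproduce. The check is a day count and a comparison of sections.

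**Inputs**
- Minimum gap between the parent's call and the recording call: 10 days (section 5.7).
- Course length: 10 days, last dose on course day 10 (sections 5.4, 6.1, 6.5).
- Reporting limit: 1 working day from PI or co-investigator awareness (section 7.4.2).
- Routine adverse event questions: every 2 months (section 5.7).

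**Day count.** Let the parent ring on course day *d*, with *d* from 1 to 10.
- Earliest recording call = *d* + 10.
- Days from last dose to that call = (*d* + 10) − 10 = *d*.

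| Parent rings on course day | Treatment days left (10 − *d*) | Earliest recording call | Days after last dose |
|---|---|---|---|
| 1 | 9 | day 11 | 1 |
| 2 | 8 | day 12 | 2 |
| 5 | 5 | day 15 | 5 |
| 10 | 0 | day 20 | 10 |

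For every *d* the recording call falls after the course has ended. The only exception is a scheduled two-monthly call that happens to fall inside the gap, since its adverse event question is not subject to the hold.

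**Against the reporting limit.** Ten consecutive calendar days are one full week (5 weekdays) plus 3 more days (1 to 3 weekdays), so 6 to 8 weekdays. This cannot be set directly against the 1 working day in section 7.4.2, because the two intervals start at different moments: the first at the parent's call, the second at investigator awareness. It shows only how far awareness could slip if the call-back were the first time the event was written down and passed on.

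**Is there another recording step?** In the text that can be read, no sentence says that the nurse records an adverse event during the parent's own call or tells the investigator about it. Section 7.3 refers to a flowchart for notification, which is not visible in the text reviewed.

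**The case against.** The strongest reply is that the hold applies to the nurse's outgoing call and not to the parent's contact. The parent speaks to the nurse on day 0, so trial staff hear the concern then, and nothing forbids the nurse from noting it or telling the investigator at once. That is correct. It rules out saying that the team stays unaware for 10 days, or that a decision under section 6.7 is necessarily taken without the information. It does not remove the defect: the written procedure assigns recording to the later call, and the protocol should not depend on staff departing from it.

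A reader might also infer that section 5.7 breaks the one-working-day rule. It does not. That limit runs from PI or co-investigator awareness, and it covers only unexpected SAEs and SUSARs. Six listed reasons for hospitalisation go in the CRF only (section 7.4.1), and the colds and wheeze that trigger treatment are not adverse events (section 7.1.1). For other events the consequence is later recording.

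Nor can it be said that no immediate route exists. The section 7.3.1 flowchart is not visible in the text reviewed and may show one; that gap is not a fault of the protocol. The emergency code break in section 5.10 is also available. If the flowchart does give an immediate route, section 5.7 would still need to be aligned with it.

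Finally, the design already accepts recall of up to about two months through its routine calls, so a call-back from day 10 will often come sooner than the next scheduled one. Parents also keep a diary, in which section 5.4 has them note vomiting after a dose. Both points reduce the loss. They do not explain why an event that a parent volunteers today should be recorded 10 or more days later.

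**Conclusion.** The point holds as a fault in a stated rule, at the level of should-fix. A medication concern raised during a course is formally recorded on course day 11 to 20 at the earliest, unless a scheduled call falls first. The rule makes no exception for a suspected reaction, and the readable text states no recording or hand-over at first contact. This weakens the timing information in the safety data and can delay investigator awareness. It is not a breach of section 7.4.2.

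The size in children cannot be given. The rule could apply to any of the 1300, but the protocol gives no rate of parent-initiated calls and no split between supply requests, for which the delay costs no safety information, and medication concerns. The day count assumes that the call is made during a course and that the call-back is made no earlier than section 5.7 allows. Sample size, power and the primary analysis are unaffected.

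**What to change.** Amend the paragraph in section 5.7 to:
1. confine the 10-day hold to the outcome and resource-use questions (days of wheeze, GP attendance, additional therapy, days lost and the like);
2. state that any adverse event volunteered in the parent's own call is recorded at that contact and passed to the PI the same working day;
3. cross-refer to sections 7.3 and 7.4.2, after checking the flowchart so that the three sections describe one route.

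The starting point of the limit in section 7.4.2 can stay as it is. Adding the parent's call to the adverse event row of the section 3.1 schedule would keep the table consistent.

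The cost is a one-paragraph amendment and a short briefing for nurses. The first contact becomes slightly longer and could marginally influence attendance in the few families who ring with a concern. The procedure would be the same in both blinded arms. The primary outcome, which section 10.1.1 has verified against clinical records, keeps its protection, because the attendance and symptom questions stay behind the hold.
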